1.0 LIST OF ABBREVIATIONS

AE	Adverse Event
CRF	Case Report Form
CRO	Contract Research Organisation
EC	Ethics Committee
FAS	Full Analysis Set
GCP	Good Clinical Practice
ICF	Informed Consent Form
ICH	International Conference on Harmonization
MedDRA	Medical Dictionary for Drug Regulatory Activities
mg	milligrams
NPRS	Numerical Pain Rating Scale
PP	Per Protocol
QA	Quality Assurance
SAE	Serious Adverse Event
SOP	Standard Operating Procedure
VRS	Visual Rating Scale
WHO-DD	World Health Organization Drug Dictionary

2.0 STUDY SYNOPSIS

Study Title	Multicentre observational study on the wound pain relief properties of ORTODERMINA®
Study Code	SINALGO
Study Sponsor	SOFAR Spa - [name]
Study Coordinator	Prof.
Study Chairman	Prof.
Participating countries	Italy
Participating centres	4 centres
Background Information and Study Rationale	Anaesthetic treatment is a common clinical problem. Acute pain may occur due to trauma, surgery, infection, disruption of blood circulation or many other conditions in which there is tissue injury. In a medical setting it is usually desirable to alleviate pain when its warning function is no longer needed. Besides improving patient comfort, pain therapy can also reduce harmful physiological consequences of untreated pain. Acute pain can often be managed using analgesics. However, conduction anaesthesia may be preferable because of superior pain control and fewer side effects. The anaesthetic properties of ORTODERMINA® and the ability to maintain the anaesthetic effect are the peculiar characteristic of this lidocaine hydrochloride formulation. Lidocaine hydrochloride is used topically to relieve itching, burning and pain from skin inflammations and it is also injected as a dental anaesthetic or as a local anaesthetic for minor surgery. Overall ORTODERMINA can improve skin tissue lesions leading to a reduction of local pain.
Study Drug	ORTODERMINA® 5%
Study Design	Observational, single-arm, multicentre
Primary Objectives	To observe wound pain relief in patients with painful wounds treated with ORTODERMINA®
Secondary Objectives	To collect safety information on ORTODERMINA® in patients with painful wounds
Primary End-points	- Wound pain relief based on a 5-point Visual Rating Scale (VRS - Appendix 1) - Pain intensity based on a 11-point Numerical Pain Rating Scale (NPRS - Appendix 2)
Secondary End-points	Incidence and severity of AEs and SAEs
Number of patients	78 patients enrolled (70 evaluable)
Inclusion Criteria:	
 • Age ≥ 18 years • Patients with painful exuding wounds $>1 \text{ cm}^2$ that includes painful exuding ulcers (and pressure ulcers grade II (according to NPUAP classification – appendix 3) • Patients available and able to return to the study site for the scheduled visits • Patients who gave written informed consent to take part into the study

Exclusion Criteria:	
 Patients with ulcer infected, discoloured, odorous, pressure ulcer grade I, III, or IV (according to NPUAP classification – Appendix 3) Diabetic foot ulcer Patients with contraindication or known allergy to drug's components Patients with known severe allergies manifested by a history of anaphylaxis, or history or presence of severe multiple allergies Female patients who are pregnant or lactating. Patients with vascular disorders (mainly arteriopathies) Patients known as alcohol or drug abusers. Patients currently participating in a clinical study
Treatment	Local treatment with ORTODERMINA® over 14 days period (once a day)
Prohibited medication	Other compounds containing Lidocaine
Planned Sample Size and Statistical Methods	
A sample size of 70 evaluable patients is needed to test the hypotheses of an improvement in wound pain relief and of a reduction in pain intensity, assuming a standardized effect size equal to 0.35, for a one-tailed test with a 5% significance level and a 90% power. Supposed that a 10% of attrition rate is expected the total number of patients to be enrolled is 78.
 
Differences in wound pain relief from baseline to end of treatment will be analysed with a one-sample t-test, assuming a reference value equal to 0 at baseline; changes in pain intensity with a two-paired samples t-test.

Planned Study Timelines:	
FPFV: First quarter 2015
 
LPLV: First quarter 2016

3.0 STUDY FLOW-CHART

ASSESSMENT/ EVENTS	V1 (Day 1)	V2 (Day 8)	V3 (Day 15)
	Screening, enrollment and start of treatment	Control Visit	End of Study
Informed consent signature	X		
Treatment administration		X (Day 1 – 14)	
Demography	X		
Inclusion/Exclusion criteria	X		
Medical and surgical history and underlying diseases	X		
Previous¹ and concomitant² medications	X ^{1,2}	X ²	X ²
Vital signs	X		X
Clinical evaluation	X		
Wound examination	X	X	X
5-point Visual Rating Scale evaluation (recorded by the patient on the Diary)		X (Day 1 -15)	
11-point Numerical Pain Rating Scale evaluation (recorded by the patient on the Diary)		X (Day 1 -15)	
AEs / SAEs		X (from the Informed Consent signature to D15)	
Patient's Diary revised by the Investigator		X	X (collected)

¹ Medications started before the patient's enrolment in the study, including the ongoing treatment.

² Medications started during the patient's participation in the study, including the ones related to AE.

4.0 INTRODUCTION AND RATIONALE

In recent years, there has been a better understanding of the acute pain process that may occur due to trauma, surgery, infection, disruption of blood circulation or many other conditions in which there is tissue injury. In a medical setting, it is usually desirable to alleviate pain when its warning function is no longer needed. Besides improving patient comfort, pain therapy can also reduce harmful physiological consequences of untreated pain. Pain represents a major problem for patients with chronic wounds (1–5). Poor management of pain has been shown to affect patients' quality of life (6,7) and potentially influences healing (8). Chronic pain in leg ulcers is often poorly managed (9), with the prevalence of pain reported as being as high as 64% (2).

A participant in one study of painful leg ulcers described his/her situation as being 'locked in a shell of pain' (7). Almost 50% of patients in one study investigating the impact of dressings and cleansing agents could not use compression dressings because of the associated pain (8). People with ulcers of venous, arterial, mixed arterial venous, and vasculitis origin are reporting serious problems with wound pain (1,2).

However, there is limited literature on the effect of active treatments in these patients.

Acute pain can often be managed using analgesics. However, conduction anaesthesia may be preferable because of superior pain control and fewer side effects.

In this context lidocaine play an important role in different pathological conditions (10, 11).

All local anaesthetics are membrane stabilizing drugs; they reversibly decrease the rate of depolarization and repolarization of excitable membranes (like nociceptors). Though many other drugs also have membrane stabilizing properties, not all are used as local anaesthetics (propranolol, for example). Local anaesthetic drugs act mainly by inhibiting sodium influx through sodium-specific ion channels in the neuronal cell membrane, in particular the so-called voltage-gated sodium channels. When the influx of sodium is interrupted an action potential cannot arise and signal conduction is inhibited. The receptor site is thought to be located at the cytoplasmic (inner) portion of the sodium channel. Local anaesthetic drugs bind more readily to sodium channels in an activated state, thus onset of neuronal blockade is faster in neurons that are rapidly firing. This is referred to as state dependent blockade(12)

Local anaesthetics are weak bases and are usually formulated as the hydrochloride salt to render them water-soluble. At a pH equal to the protonated base's pKa, the protonated (ionized) and unprotonated (unionized) forms of the molecule exist in equimolar amounts but only the unprotonated base diffuses readily across cell membranes. Once inside the cell the local anaesthetic will be in equilibrium, with the formation of the protonated (ionized form), which does not readily pass back out of the cell. This is referred to as "ion-trapping". In the protonated form, the molecule binds to the local anaesthetic binding site on the inside of the ion channel near the cytoplasmic end.

Acidosis such as caused by inflammation at a wound partly reduces the action of local anaesthetics. This is partly because most of the anaesthetic is ionized and therefore unable to cross the cell membrane to reach its cytoplasmic-facing site of action on the sodium channel.

All nerve fibres are sensitive to local anaesthetics, but due to a combination of diameter and myelination, fibres have different sensitivities to local anaesthetic blockade, termed "Differential Blockade." Type B fibres (sympathetic tone) are the most sensitive followed by Type C (Pain), Type A delta (temperature), Type A gamma (proprioception), Type A beta (sensory touch and pressure) and Type A alpha (motor). Although Type B fibers are thicker than Type C fibers, they are myelinated, and thus are blocked before the unmyelinated, thin C Fiber. (13)

The properties of ORTODERMINA® and the ability to maintain adequate levels of Lidocaine over the lesions, allow a durable anaesthetic effect. ORTODERMINA® is a drug for topical application in the form of cream.

The drug has a high safety profile and although the incidence of adverse effects with Lidocaine Ointment 5% is quite low, caution should be exercised, particularly when employing large amounts, since the incidence of adverse effects is directly proportional to the total dose of local anaesthetic agent administered.

5.0 STUDY OBJECTIVES

5.1 Primary Objectives

- To observe wound pain relief in patients with painful wounds treated with ORTODERMINA®

5.2 Secondary Objectives

- To collect safety information on ORTODERMINA® in patients with painful wounds.

6.0 STUDY END-POINTS

6.1 Primary End-points

- Wound pain relief based on using a 5-points Visual Rating Scale (14) (Appendix 1)
- Pain intensity based on a 11-point Numerical Pain Rating Scale (15) (Appendix 2)

6.2 Secondary End-points

- AEs occurred over the study period (from the Informed Consent signature to the V3) will be registered.

7.0 STUDY DESIGN

This is an observational, single-arm, multicentre study.

7.1 Duration of Clinical Investigation

After having signed the Informed Consent the patients will undergo a screening visit; patients fulfilling the inclusion/exclusion criteria will be enrolled in the study and treated once a day with ORTODERMINA® throughout a period of 14 days in addition to any therapy the physician will have prescribed for the treatment of the lesion.

8.0 STUDY POPULATION

8.1 Number of patients

A total number of 78 patients will be enrolled (70 patient evaluable) in the study.

8.2 Selection of patients

8.2.1 Inclusion criteria

Subjects must meet all the following inclusion criteria to be eligible for enrolment into the study:

- Age \geq 18 years

- Patients with painful exuding wounds >1 cm² that includes painful exuding ulcers and pressure ulcers grade II (according to NPUAP classification – Appendix 3)
- Patients available and able to return to the study site for the scheduled visits
- Patients who gave written informed consent to take part into the study

8.2.2 *Exclusion Criteria*

The presence of any following will exclude a subject from study enrolment:

- Patients with ulcer infected, discoloured, odorous, pressure ulcer grade I, III, or IV (according to NPUAP classification – Appendix 3)
- Diabetic foot ulcer
- Patients with contraindication or known allergy to drug's components or to the treatment
- Patients with known severe allergies manifested by a history of anaphylaxis, or history or presence of severe multiple allergies
- Female patients who are pregnant or lactating
- Patients with vascular disorders (mainly arteriopathies)
- Patients known as alcohol or drug abusers
- Patients currently participating in a clinical study

8.3 *Screening and Enrolment Procedures*

Before any screening procedure the patient must have signed and dated a written informed consent for the study. Then the Investigator assigns the patient study number that is progressive within the centre (preceded by the centre number).

If the patient is eligible for the study the notification of patient registration in the study is submitted to Eudax ([contact]) using the "Subject Registration Form".

The following logs must be maintained at each study site and kept in the Investigator File:

- ✓ "Subject Screening and Enrolment Log" to register all subjects who enter screening and to document chronological enrolment of patients. In case of screening failure the reason(s) for failure will be also documented on the CRF and on the source documents (hospital records).
- ✓ "Subject Identification Log" for all subjects registered to maintain the correlation with the patient's full identification data (subject study number, name, surname, number of the subject's hospital record - confidential)

8.4 Discontinuation/ Withdrawals of patients from study treatment

Patients will be withdrawn at any time from the study at their own request or at the discretion of the Investigator if considered necessary in the best patient's interest. The reason for withdrawals/drop-outs must be fully documented in the CRFs as well in source documents.

8.5 Replacements

Withdrawals/drop-outs patients will be replaced in order to have a total of 70 evaluable patients.

9.0 STUDY PRODUCT

9.1 Drug Supply

Due to the observational nature of the study, ORTODERMINA® will be prescribed according to clinical practice.

9.2 Drug Administration

ORTODERMINA® is available in 50 g laminate tubes with a child-resistant cap,

A single application of ORTODERMINA® should not exceed 5 g of Lidocaine Ointment 5%. This is roughly equivalent to squeezing a fifteen (15) cm length of ointment from the tube.

9.3 Drug Compliance

The patient will be required to record in the diary the daily ointment application during the study period (Day 1-14). Only the patients compliant with at least the 80% of the applications (at least 11 treatment days) will be included in the efficacy analysis.

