12.6 Safety data

The safety analysis population will include all patients who received at least one dose of treatment and had a safety assessment performed at baseline. All safety parameters will be summarized and presented in tables based on this safety population.

Adverse event data will be presented in frequency tables (overall and by intensity) by System Organ Class and Preferred Term (MedDRA dictionary). In tables showing the overall incidence of adverse events, patients who experienced the same event on more than one occasion are counted only once in the calculation of the event frequency.

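### The plan records the days on which the product was applied, but not the amount used or the number of applications in a day, so the dose behind the adverse-event rates will be unknown

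*Combined protocol and SAP*

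**What the plan says.** **What is recorded.** Section 9.3 (Drug Compliance) says: "The patient will be required to record in the diary the daily ointment application during the study period (Day 1-14"). It then sets a compliance threshold of 80% of applications, which it equates with 11 treatment days. Section 14.2 lists drug compliance among the diary contents without describing it further.

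**Why amount matters to this protocol.** Section 4.0 advises care with large amounts, "since the incidence of adverse effects is directly proportional to the total dose of local anaesthetic agent administered". Section 9.2 caps a single application at 5 g and gives a conversion from length to weight: "This is roughly equivalent to squeezing a fifteen (15) cm length of ointment from the tube".

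**Frequency and limits.** Section 7.1 has patients "treated once a day with ORTODERMINA® throughout a period of 14 days", and the synopsis agrees. Section 9.1 says that the product "will be prescribed according to clinical practice". Appendix 4 section 4.2 gives no fixed amount per application and caps daily use at 35 g.

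**Safety analysis.** Section 12.6 says: "Adverse event data will be presented in frequency tables (overall and by intensity) by System Organ Class and Preferred Term". It plans no summary of exposure.

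**The concern.** The protocol names total dose as the driver of adverse effects and sets a limit on amount, but the data it plans to collect cannot give a patient's total dose or show whether a limit was kept. Safety is the only secondary objective. A low adverse-event rate means one thing if patients used a small amount once a day and another if they used much more, and the report could not say which applies.

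The amount is likely to differ between patients. Section 8.2.1 admits wounds above 1 cm² with no upper size limit, and no section fixes the amount to apply. Amounts and within-day applications not recorded during the 14 days cannot be reliably reconstructed at analysis.

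**Working it through.** **Step 1. Look for any record of amount or of applications within a day.**

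- Flow-chart (section 3.0): treatment administration on Days 1 to 14; no amount.
- Visit lists (10.1 to 10.3): first administration, diary distribution and review; no amount, no product count.
- Compliance (9.3): daily application; no amount, no count within the day.
- Diary contents (14.2): drug compliance; no amount.
- Adverse-event documentation (11.3): dates, outcome, intensity, action taken, relationship; no dose.
- Safety analysis (12.6): event tables; no exposure summary.

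None of these asks for grams, length, or number of applications in a day.

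**Step 2. Check the compliance rule.** 80% of 14 days is 0.80 × 14 = 11.2 days. The stated 11 days is 11/14 = 78.6%, slightly under 80%; 12 days would be 12/14 = 85.7%. As written, the rule counts treatment days, has a lower bound and has no upper bound.

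**Step 3. Total product at the stated ceilings.** Inputs: 5 g per application (9.2), once a day for 14 days (7.1), 35 g per day (Appendix 4 section 4.2), 5 g lidocaine base per 100 g of cream (Appendix 4 section 2).

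- 5 g once daily: 5 × 14 = 70 g of product, or 70 × 0.05 = 3.5 g lidocaine base.
- 35 g daily: 35 × 14 = 490 g of product, or 490 × 0.05 = 24.5 g lidocaine base.
- Ratio: 490/70 = 7.

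**Step 4. Spread among patients who all meet the compliance rule.**

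- 5 g on 11 days: 5 × 11 = 55 g.
- 35 g on 14 days: 490 g.
- Ratio: 490/55 = 8.9. With 12 days as the minimum it would be 490/60 = 8.2, so the reading of the 80% threshold hardly matters here.

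**Step 5. Are the two ceilings contradictory?** Not strictly: seven applications of 5 g make 35 g. But with one application a day, section 9.2 implies at most 5 g daily, while Appendix 4 allows 35 g. The limits have different bases and the protocol does not say how they fit together.

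**The case against.** Much can be said for the plan, and most of it stands.

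- *The safety objective is descriptive.* Section 5.2 only sets out to collect safety information. Incidence, intensity, causality and action taken are recorded per event and can be reported without grams. A reader might infer that the safety objective cannot be interpreted at all; the documents do not support that. What is lost is the dose to which the rates apply and any link between events and dose.
- *Some exposure is measured.* Days of application are recorded, so it would be wrong to say that exposure is not measured. The gap is in amount and within-day frequency.
- *The frequency is consistent.* The synopsis and section 7.1 say once a day, and section 9.3 refers to daily application. Section 9.1 is headed Drug Supply and plausibly means only that the product comes through routine prescription. It states no rival frequency, so two conflicting regimens cannot be read from it. The wording is loose, and the ceilings in section 9.2 and Appendix 4 are the figures that most need to be aligned.
- *Over-use could still be classed as a deviation.* The major deviations in section 12.3 are examples, and the investigator reviews the diary at Visits 2 and 3. It therefore does not follow that every over-user would be counted as compliant and kept in the per-protocol set. But no planned data item would bring such use to light.
- *The upper figure is extreme.* The 35 g daily limit covers all uses of the product, including oral and perianal use. Over 14 days it means 490/50 = 9.8 tubes of 50 g, and at 5 g each it means seven applications a day. It is a ceiling. A still wider ratio follows if one assumes a small amount, such as 1 g a day (14 g in total, 490/14 = 35-fold), but the documents give no such figure.
- *The diary form is not in the documents.* It may contain a field for amount. Sections 9.3 and 14.2 do not require one.

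**Conclusion.** The point holds as a gap in data collection that is cheap to close. The plan captures days of application but neither the amount used nor the number of applications in a day, against its own statement that adverse effects rise in proportion to total dose. Adverse-event incidence remains reportable; the dose it describes will be unknown, and use above either stated limit would be invisible in the planned data.

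The size is 7-fold between the stated ceilings over 14 days, and 8.9-fold between two patients who both satisfy the compliance rule. Both figures are bounds drawn from limits in the documents, not estimates of actual use, for which the documents give no figure. The conclusion assumes that the diary contains no more than sections 9.3 and 14.2 describe. It does not threaten the primary efficacy analysis.

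**What to change.** 1. **Sections 9.3 and 14.2:** add two daily diary fields, the number of applications and the approximate length of product used.
2. **Section 12.6:** add a descriptive exposure table (applications and approximate total amount per patient), and a listing that shows the patient's exposure alongside each adverse event.
3. **Reconciliation:** the sponsor should align sections 7.1, 9.1, 9.2 and Appendix 4 section 4.2 on frequency and maximum amount, then summarise recorded use against whatever limit it confirms. Which limit applies is for the sponsor to state. Section 9.2 gives its conversion for an ointment, while section 4.0 and Appendix 4 describe a cream, so the sponsor should also confirm that the conversion fits the product used.

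The cost is two short entries in a diary that patients already complete daily and the investigator already reviews, plus one table and one listing. The downside is slight diary burden and imprecise self-reported lengths, since section 9.2 itself calls the conversion rough. The amounts should be labelled approximate.

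Two additions are not worth making. Weighing tubes adds a procedure and is awkward when tubes are prescribed in routine practice. Comparing adverse events across thirds of total amount would leave about 78/3 = 26 patients per group, with few events and probable confounding by wound size.

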9.4 Concomitant Medication

Other compounds containing Lidocaine will not be allowed for the entire study period. Patient using other compound containing Lidocaine during the study will be excluded from the efficacy analysis.

Any additional treatment/medication including any compound prescribed for the routine treatment of the target lesion, taken by the patient during study period, started before the patient's enrolment in the study (ongoing treatment) or started during the patient's participation in the study will be report in the CRF. The patient will be required to record in the diary any new medication used during the study period (Day 1-14).

